Concomitant therapy		X	X	X	X	X	$X^3$	X
Medication wash-out		X	X	X	X	X	X	

Boehringer Ingelheim 15 APR 2016

BI Trial No.: 1237.28

c03207491-01 Trial Protocol Page 9 of 137

Proprietary confidential information © 2016 Boehringer Ingelheim International GmbH or one or more of its affiliated companies

		Screening				Treatment Period1		
Visit	0	1	2	3	4, 7	5, 8	6, 9 (V9- EOT)	10
Week of treatment	1	1	-	-	0	3	6	V9-EOT + 3 weeks
Day of treatment Time Window (days)	-	-21 to -14	-13 to -9	-8 to -1	1	22 +7	43 + 7	V9-EOT + 21 + 7
Rescue Medication Use		X	X	X	X	X	$X^3$	
Trial Medication Adherence 						X	$X^3$	
Telephone contacts 		X	X	X	X	X	X	
Trial medication termination							X  (call IRT at V9 only)	
Trial completion								X

- 1. Treatment Period: In this cross-over design, each treatment period (period 1, period 2) will follow the same flow chart:
  - procedures during visits 4 and 7 will be identical (except for inclusion/exclusion check, randomisation and BDI at V4 only)
  - procedures during visits 5 and 8 will be identical
  - procedures during visits 6 and 9 will be identical
- 2. Informed Consent: All patients must sign an informed consent consistent with ICH-GCP guidelines prior to participation in the trial, which includes medication washout and restrictions.
- 3. Procedures: To be completed at the end of each treatment period and / or by all patients who took at least one dose of trial medication including those who discontinue early. PFTs are to be performed if possible.
- 4. Pregnancy Testing: Women of child-bearing potential: serum pregnancy test at visit 1; urine pregnancy test at visits 4, 6, 7, 9, 10.
- 5. ECG: 12-lead ECG recording at screening (visit 1) and end of treatment periods (visits 6 and 9) to be measured pre-dose.
- 6. Body Plethysmography: Conducted prior to dosing with salbutamol for inclusion.
- 7. Device Training: The patient will be instructed in the use of the Respirat® inhaler, but the patient **should not** inhale from the placebo inhaler at these visits.
- 8. Rescue Medication: To be supplied to all patients starting at visit 0.
- 9. Trial Medication Collection: Last dose of trial medication for the respective treatment period will be the morning dose, taken in the clinic on Day 43. All medication is collected after this dosing.

Boehringer Ingelheim BI Trial No.: 1237.28

c03207491-01

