15 APR 2016
BI Trial No.: 1237.28

c03207491-01 Trial Protocol Page 22 of 137

Proprietary confidential information © 2016 Boehringer Ingelheim International GmbH or one or more of its affiliated companies

A secondary objective is to explore the relationship between reductions in breathlessness during the 3min CSST and reductions in breathlessness during activities of everyday living as measured by the dyspnea domain of the Chronic Respiratory Questionnaire (CRQ) following bronchodilator therapy.

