### CHRONIC RESPIRATORY QUESTIONNAIRE SELF-ADMINISTERED INDIVIDUALIZED FORMAT (CRQ-SAI) FIRST ADMINISTRATION

i. Please read the following list of activities which make some people with lung problems feel short of breath. Place an "x" in the box beside each activity IF you answer YES to ALL of the following four statements: you have done the activity during the LAST 2 WEEKS and it is something you do frequently and it is important to your day to day life and it makes you feel short of breath

- If you have not done the activity during the LAST 2 WEEKS or it does NOT make you feel short of breath then leave it blank.
- iii. After you have read the list, please add any additional activities in the spaces provided.

  Only write down additional activities IF you answer YES to ALL of the following four statements:

  you have done the activity during the LAST 2 WEEKS and it is something you do frequently and it is important to your day to day life and the sy you feel short of breath

PLACE AN "X" IN THE BOX BESID AT ACTIVITIES T	THAT APPLY	
1 BEING ANGRY OR UPSET	13 PLAYING WITH CHILDREN OF	GRANDCHILDREN
2 HAVING A BATH OR SHOWER	PLAYING SPORTS	
3 BENDING	REACHING OVER YOUR HEAD	0
4 CARRYING, SUCH AS CARRYING GROCER 25	NNING, SUCH AS FOR A B	US
5 DRESSING	PPING	
6 EATING	18 WHIP AYING TO SLEEP	
7 GOING FOR A WALK	19 🔲 NG	
8 DOING YOUR HOUSEWORK	20 ACL NG	
9 HURRYING	21 WALKING OUT ON	/N HOME
10 MAKING A BED	22 WALKING UPHI	
11 MOPPING OR SCRUBBING THE FLOOR	23 WALKING UPSTA	
12 MOVING FURNITURE	24 WALKING WITH OTHERS ON I	LEVEL GROUND

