5.2.2 Secondary endpoints

Secondary endpoints of efficacy will be used as described in the CTP, Section 5.1.2.

CRQ scores are calculated according to “CRQ Package_English” [\(1\)](#).

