6.6 HANDLING OF MISSING DATA AND OUTLIERS

As noted in the protocol, in general, missing data at a given visit will be imputed by the available data from the patient at that visit and completely missing visits will be handled through the statistical model.

Completely missing visits not due to worsening of study disease will not be imputed and will stay as missing, because such missing data are considered as randomly missing data and will be handled in the mixed model repeated measures model.

Completely missing visits due to the patient discontinuing due to worsening of study disease will be imputed with the least favourable prior visit during that period.

It could happen that a patient needed therapy for COPD symptoms at a clinic visit. This therapy was entered on the rescue medication electronic Case Report Form (eCRF). This may or may not be the rescue medication provided by Boehringer Ingelheim (BI). For purposes of the imputation rules this will be termed “rescue medication” regardless of whether or not it was BI-supplied rescue medication.

The following rules are used for exercise data:

In situations where the full 3-min of exercise was completed:

- Measurements of Borg breathing discomfort scale, [REDACTED] which are missing for the 3 minute time point will be imputed using the last non-missing observation during exercise (but not non-missing measurements at rest) for that visit.
- Measurements of Borg breathing discomfort scale, [REDACTED] which are missing for all other time points during exercise will not be imputed (i.e. left as missing).

In situations where exercise is terminated prematurely:

- Borg breathing discomfort [REDACTED] scores will be imputed from end-of-exercise value for all time points beyond the exercise termination (including the 3 minute time point).

[REDACTED]

In addition, the following rules apply:

[REDACTED]

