- If rescue medication was used prior to exercise testing or if the time of rescue medication use is unknown, measurements taken at rest and during exercise, i.e., - Borg scale of breathing discomfort, [REDACTED] blood pressure, and IC will be set to missing and not imputed. If rescue medication was used during exercise testing, measurements of Borg scale of breathing discomfort [REDACTED] will be set to missing for those time points after the first use of rescue medication and imputed using the worst non-missing observation during exercise (but not non-missing measurements at rest) for that visit before rescue medication use.

The following rules will be used for spirometry data which were collected at Visits 4, 5, 6, 7, 8, and 9:

- Since there is only one spirometry measurement at each on-treatment clinic visit, rescue medication use on or before the spirometry measurement or rescue use with unknown time will both result in all spirometry measurements for the visit being set to missing. In these cases the entire visit will be imputed using the least favourable prior non-missing measurement from previous visits during that period.
- If the spirometry measurement for a visit is completely missing because a patient discontinued due to worsening of study disease, then all data for this visit will be imputed with the least favourable prior observation from previous visits during that period.
- Randomly missing spirometry measurements at Visits 5, 6, 8 and 9, e.g., due to a mechanical failure, will not be imputed.

Also,

[REDACTED]

- For endpoints with two period baselines, if one period baseline is missing, it will be imputed by the other period baseline.

- For CRQ-SAI, at visits where dyspnoea activities were selected differently than the baseline (at visit 4), those dyspnoea activity values will be set as missing values.

Missing or incomplete AE dates are imputed according to BI standards (see “Handling of missing and incomplete AE dates”) [\(2\)](#).

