6.7 BASELINE, TIME WINDOWS AND CALCULATED VISITS

Period baseline

The period baseline is defined as the pre-dose measurement, performed prior to dosing on the first day of each period.

Patient baseline

The patient baseline is defined as the mean of non-missing period baselines for each patient.

Study baseline

For endpoints with only one baseline measurements prior to the first treatment period, this baseline will be called study baseline.

More specifically,

Baselines for Primary Endpoint

The primary endpoint is the change from baseline in intensity of breathlessness measured using the MBS-S at the end of the 3min Constant Speed Shuttle Test (CSST) after 6 weeks of treatment.

- Period baselines are measured at the end of the 3 min CSST at visits 4 and 7

Period Baselines for Secondary Endpoints

Change from baseline in Inspiratory Capacity (IC) measured prior to exercise, after 6 weeks of treatment.

- Period baselines are measured in resting IC (Omnia) prior to exercise at visits 4 and 7

Change from baseline in IC measured at the end of exercise, after 6 weeks of treatment

- Period baselines are measured in IC at the end of exercise at visits 4 and 7

Change from baseline in 1 hour post-dose FEV₁, after 6 weeks of treatment.

- Period baselines are measured in pre-dose FEV₁ at visits 4 and 7

Change from baseline in 1 hour post-dose FVC, after 6 weeks of treatment.

- Period baselines are measured in pre-dose FVC at visits 4 and 7

Change from baseline in intensity of Breathlessness (MBS-S) at 1min, 2min, and 2.5min during the 3min CSST after 6 weeks of treatment.

- Period baselines are measured at the corresponding time point during the 3 min CSST at visits 4 and 7

Change from baseline in Chronic Respiratory Questionnaire - Self Administered Individualized (CRQ-SAI) dyspnea domain score after 6 weeks of treatment.

- Period baselines are collected at visits 4 and 7

Change from baseline in Chronic Respiratory Questionnaire - Self Administered Standardized (CRQ-SAS) dyspnea domain score after 6 weeks of treatment.

- Period baselines are collected at visits 4 and 7

[REDACTED]

[REDACTED]

[REDACTED]

[REDACTED]

[REDACTED]

[REDACTED]

[REDACTED]

[REDACTED]

Time windows and calculated visits

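### SAP 6.6 blanks CRQ-SAI ratings of activities that differ from Visit 4 but does not put the baseline, or the other period's score, on the same activities

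*SAP*

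**What the plan says.** SAP 6.6 has one bullet on the CRQ-SAI: at visits where "dyspnoea activities were selected differently than the baseline (at visit 4), those dyspnoea activity values will be set as missing values". It names Visit 4 as the only reference and says nothing about the score at Visit 4 itself.

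SAP 6.7 says of the CRQ-SAI that "Period baselines are collected at visits 4 and 7", and in general that "The patient baseline is defined as the mean of non-missing period baselines for each patient". It does not mention matching activities. Visit 7 is therefore both a baseline visit and a visit that the blanking rule reaches. Protocol 5.1.1 takes change from the patient baseline; it says so for the primary endpoint, and SAP 7.5.2 applies the same model to the secondary endpoints.

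On scoring, SAP 5.2.2 says only "CRQ scores are calculated according to" a CRQ package that is not part of the documents. SAP 6.6 also has a general rule that "missing data at a given visit will be imputed by the available data from the patient at that visit", without saying whether it covers blanked CRQ-SAI activities.

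On selection, protocol 5.2 has patients choose five activities that matter to them. Flow Chart footnote 1 says "procedures during visits 4 and 7 will be identical", with three exceptions that do not include the CRQ-SAI. The only CRQ-SAI form visible in Appendix 10.10 is the first-administration form. It tells the patient that if an activity was not done in the past two weeks or "it does NOT make you feel short of breath then leave it blank".

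**The concern.** An individualised score is interpretable as a change only if the same activities are rated on each occasion. The SAP rule recognises that lists may differ and removes the non-matching ratings, but only at the visit where the mismatch occurs. The baseline can keep five activities while Visit 6 keeps three or four, and Visit 9 may keep a different subset. The difference then mixes a change in breathlessness with a difference in how demanding the remaining activities are.

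Two results are exposed. One is the CRQ-SAI treatment contrast, a named secondary endpoint in protocol 5.1.2. The other is the secondary objective in protocol 2.2, which relates the reduction in breathlessness on the 3min CSST to the reduction on the CRQ dyspnea domain. That analysis uses individual changes, so a mismatch with the baseline enters it directly.

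**Working it through.** **What can be checked.** The documents give no CRQ-SAI mean, SD, effect size or re-selection rate, so there is no stated figure to reproduce for this endpoint. The sample size concerns the primary endpoint and is unaffected. Everything below is illustrative. Assumption throughout: domain score = mean of the rated activities on the 1 to 7 scale, higher is better.

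**1. One patient, change from baseline.** Visit 4 ratings are 2, 3, 3, 4, 4, mean 16/5 = 3.2. Visit 7 is taken to repeat them, so the patient baseline is 3.2.

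- *An improved activity is lost.* Visit 6 is 3, 4, 4, 5, 7, mean 23/5 = 4.6; true change 4.6 − 3.2 = 1.4. Blank the activity now rated 7: 16/4 = 4.0. Change against the full baseline: 4.0 − 3.2 = **0.8**. Against the same four activities (12/4 = 3.0): **1.0**.
- *A worsened activity is lost.* Visit 6 is 1, 4, 4, 5, 5, mean 19/5 = 3.8; true change 0.6. Blank the activity rated 1: 18/4 = 4.5. Change against the full baseline: **1.3**. Against the same four (14/4 = 3.5): **1.0**.

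The error can go either way. Matching reduces it but does not remove it.

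**2. One patient, treatment contrast.** Let the same patient score 3, 4, 4, 5, 7 at Visit 6 and 1, 4, 4, 5, 5 at Visit 9. The full contrast is 4.6 − 3.8 = 0.8. Blank the fifth activity at Visit 6 only: (4.0 − 3.2) − (3.8 − 3.2) = **0.2**. The baseline cancels; the error comes from comparing four activities with five. On the same four at both visits: 4.0 − 14/4 = 4.0 − 3.5 = **0.5**.

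**3. Do the other rules repair this?** Filling the blank in the first example with the mean of the other four ratings gives (16 + 4)/5 = 4.0, the same score as before. A package that averages rated items gives the same. A package that needs every activity would lose the visit.

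**4. Random loss.** Losing k of 5 activities at random at one visit adds error with SD s·√(1/(5−k) − 1/5), where s is the SD between activities. With s = 1 this is 0.22, 0.37, 0.55 and 0.89 for k = 1 to 4. It is noise, not bias.

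**5. Simulated change scores.** 200,000 patients per scenario; mean 3.6, patient SD 0.8, activity SD 0.9, occasion SD 0.4, rating noise SD 0.7; true effects 0.4 (combination) and 0.2 (tiotropium); Visit 4 as baseline. Without loss the mean changes are about 0.41 and 0.21, and the difference about 0.19. The activities in the first column are blanked with probability 0.2 to 0.8; random loss is 5% to 20% of activities.

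| Activities lost | Change, combination | Change, tiotropium | Difference, SAP rule | Difference, matched to baseline |
|---|---|---|---|---|
| Rated 6 or 7 | 0.36 to 0.18 | 0.17 to 0.03 | 0.19 to 0.15 | 0.19 to 0.18 |
| Rated 1 or 2 | 0.45 to 0.63 | 0.27 to 0.48 | 0.19 to 0.16 | 0.19 to 0.18 |
| At random | 0.41 | 0.21 to 0.22 | 0.19 | 0.19 |

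The two change columns are under the SAP rule.

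**6. Simulated crossover contrast.** Mean rating 3 to 4, patient SD 0.8, activity SD 1.0, rating noise SD 0.7, effects 0.6 and 0.3; every patient loses every activity rated 7, or every activity rated 1. The contrast on all activities is about 0.29. Under the SAP rule it is 0.23 to 0.27, a loss of 0.06/0.29 = 21% down to 0.02/0.29 = 7%. With Visits 6 and 9 scored on common activities it is 0.27 to 0.28, a loss of 7% to 3%. With 15% of activities lost at random (mean 3.5) both methods are unbiased, and the SD of the contrast is 0.60 under the rule and 0.58 with common activities.

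**The case against.** A reader might infer that the rule drops the activities that improved, and so understates benefit, most on the better treatment. The documents do not support that. The selection instruction is on the first-administration form, and it also excludes activities not done in the past two weeks, which a patient may have given up because of worsening. Step 1 shows the second case inflating the change. Nor would an activity rated 6 be left off under that instruction: on this scale 6 still records some breathlessness and only 7 records none. The rows of step 5 that blank ratings of 6 therefore overstate that mechanism.

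A reader might also infer that the unmatched baseline biases the treatment comparison. It largely does not: the same patient baseline is subtracted in both periods, so apart from its role as a covariate it cancels. What remains is the mismatch between Visit 6 and Visit 9.

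Two further points stand in part. A CRQ-SAI follow-up form may exist in pages that are not visible and may already carry the Visit 4 activities forward, as the CRQ-SAS follow-up form re-presents its fixed list; mismatches would then be rare. And the absence of a matching rule is read from silence, since the scoring package cannot be seen. But the SAP did write a rule for differing lists, and neither averaging nor same-visit imputation makes the sets comparable.

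**Conclusion.** The concern holds in a limited form. Followed as written, SAP 6.6 lets individual CRQ-SAI changes, and the Visit 6 versus Visit 9 contrast, rest on different activities. Rating-dependent loss distorts the change score in a direction the documents do not settle, and it shrank the contrast in both directions simulated. Random loss adds noise only. The 7% to 21% shrinkage assumes that every patient loses every activity at the extreme rating, with invented means and variances; with rare mismatches it would be close to nil.

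The reach is narrow. The primary endpoint and sample size are untouched, the CRQ-SAI p-values are descriptive, and the CRQ-SAS, with five fixed activities, covers the same domain and is not subject to this rule. The secondary objective is more exposed where it uses the CRQ-SAI, because individual changes do not benefit from the cancellation. This is a worthwhile clarification and not a threat to the trial's main conclusion.

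**What to change.** In SAP 6.6 and 6.7, replace the CRQ-SAI bullet with a scoring rule:

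- Compute each patient's score at Visits 6 and 9, and the baseline it is compared with, on one set of Visit 4 activities: those rated at both Visit 6 and Visit 9 where both are available, otherwise those rated at the single available post-baseline visit.
- State the minimum number of activities for a valid score, and treat the score as missing below it.
- Report the number of blanked activities by treatment and visit.

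Unless the follow-up form already does this, state in protocol 5.2 and 6.2.2 that the Visit 4 activities are carried forward and re-rated at Visits 6, 7 and 9, and exempt activity selection from the Flow Chart footnote that makes Visits 4 and 7 identical. Carrying the list forward is the better protection, because it prevents the loss; matched scoring only limits its effect.

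The cost is a short SAP text, a few lines of derivation code and a site instruction, with no extra patients or visits. The downside is that patients with differing lists are scored on fewer activities, and a few may fall below the minimum.

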6.7 BASELINE, TIME WINDOWS AND CALCULATED VISITS

Period baseline

The period baseline is defined as the pre-dose measurement, performed prior to dosing on the first day of each period.

Patient baseline

The patient baseline is defined as the mean of non-missing period baselines for each patient.

Study baseline

For endpoints with only one baseline measurements prior to the first treatment period, this baseline will be called study baseline.

More specifically,

Baselines for Primary Endpoint

The primary endpoint is the change from baseline in intensity of breathlessness measured using the MBS-S at the end of the 3min Constant Speed Shuttle Test (CSST) after 6 weeks of treatment.

- Period baselines are measured at the end of the 3 min CSST at visits 4 and 7

Period Baselines for Secondary Endpoints

Change from baseline in Inspiratory Capacity (IC) measured prior to exercise, after 6 weeks of treatment.

- Period baselines are measured in resting IC (Omnia) prior to exercise at visits 4 and 7

Change from baseline in IC measured at the end of exercise, after 6 weeks of treatment

- Period baselines are measured in IC at the end of exercise at visits 4 and 7

Change from baseline in 1 hour post-dose FEV₁, after 6 weeks of treatment.

- Period baselines are measured in pre-dose FEV₁ at visits 4 and 7

Change from baseline in 1 hour post-dose FVC, after 6 weeks of treatment.

- Period baselines are measured in pre-dose FVC at visits 4 and 7

Change from baseline in intensity of Breathlessness (MBS-S) at 1min, 2min, and 2.5min during the 3min CSST after 6 weeks of treatment.

- Period baselines are measured at the corresponding time point during the 3 min CSST at visits 4 and 7

Change from baseline in Chronic Respiratory Questionnaire - Self Administered Individualized (CRQ-SAI) dyspnea domain score after 6 weeks of treatment.

- Period baselines are collected at visits 4 and 7

Change from baseline in Chronic Respiratory Questionnaire - Self Administered Standardized (CRQ-SAS) dyspnea domain score after 6 weeks of treatment.

- Period baselines are collected at visits 4 and 7

[REDACTED]

[REDACTED]

[REDACTED]

[REDACTED]

[REDACTED]

[REDACTED]

[REDACTED]

[REDACTED]

Time windows and calculated visits

Planned and actual study day will be included in the analysis data sets. These will both be calculated relative to the beginning of the study and to the beginning of respective study periods in the crossover design as indicated in the following table ([Table 6.7: 1](#)).

Table 6.7: 1 Planned and actual study days

Visit	Relative to period start		Relative to study start	
	Planned day	Actual day	Planned day	Actual day
4	1	1	1	1
5	22	Visit 5 date - Visit 4 date + 1	22	Visit 5 date - Visit 4 date + 1
6	43	Visit 6 date - Visit 4 date + 1	43	Visit 6 date - Visit 4 date + 1
7	1	1	64	Visit 7 date - Visit 4 date + 1
8	22	Visit 8 date - Visit 7 date + 1	85	Visit 8 date - Visit 4 date + 1
9	43	Visit 9 date - Visit 7 date + 1	106	Visit 9 date - Visit 4 date + 1

7. PLANNED ANALYSIS

For End-Of-Text tables, the set of summary statistics is: N / Mean / Standard deviation (SD) / Min / Median / Max.

Tabulations of frequencies for categorical data will include all possible categories and will display the number of observations in a category as well as the percentage (%) relative to the respective treatment group (unless otherwise specified, all patients in the respective patient set whether they have non-missing values or not). Percentages will be rounded to one decimal place. The category missing will be displayed only if there are actually missing values.

